10.2 Subject Disposition, Demographics and Baseline Characteristics

Subject disposition will be summarized and listed for Parts A and B separately.

The demographic variables age, sex, child-bearing potential, race, ethnicity, body weight, height, and body mass index will be summarized and listed for Parts A and B separately.

The duration history of type I diabetes mellitus will be calculated based on the information provided on the medical history electronic case report form (eCRF).

The baseline medical history and concomitant medications will be summarized by Medical Dictionary for Regulatory Activities (MedDRA) system organ class and preferred term and World Health Organization (WHO) Anatomical Therapeutic Chemical (ATC) codes for each treatment group, respectively. These data will also be listed for Parts A and B separately.

10.3 Efficacy and Pharmacodynamic Assessments

10.3.1 Efficacy Primary Endpoint

- Change from baseline at Week 12 in daily insulin use.

10.3.2 Secondary Pharmacodynamic Endpoints

- Change from baseline at Week 13 in fasting glucose and glucose AUC after the MMTT – Part A only.
- Change from baseline at Week 12 in average daily 24-h blood glucose concentration and time within target range as assessed by CGM and seven-point glucose profile.
- The product of the ratio of average glucose (Week 12/Baseline) and ratio of average insulin use (Week 12/Baseline).
- Change from baseline at Day 85 (Week 13) in HbA1c.
- Proportion of subjects who achieve HbA1c reduction of $\geq 0.4\%$.
- Change from baseline at Day 85 (Week 13) in fasting C-peptide and C-peptide AUC after MMTT and arginine challenge (for a subset of subjects who were enrolled prior to Protocol Amendment #1) – in Part A only.
- Change from baseline at Day 85 (Week 13) in peripheral levels of fasting glucagon, active and total GLP-1, and glucagon and GLP-1 (active and total) AUC after MMTT challenge – in Part A only.

10.3.3 Exploratory Endpoints

- Change from baseline at Day 85 (Week 13) in body weight.
- Change from baseline in QOL score at Day 84 (Week 13).
- Changes in intrahepatic lipid content as measured by MRI-PDFF (for a subset of subjects in Part B only)
- Changes in intrahepatic lipid content as measured by FibroScan® (for a subset of subjects in Part B only who underwent Fibroscan at baseline and post-treatment)

10.3.4 Efficacy and Pharmacodynamic Statistical Methodology

10.3.4.1 General

All data, including derived parameters, will be listed and summarized for Part A and B separately. Absolute changes (and percentage changes, where applicable) from baseline will also be listed and summarized. Values outside the reference ranges will be flagged, if appropriate.

Preliminary analyses of variance will be performed to assess whether the baseline average daily insulin use and HbA1c levels among subjects are similar between the treatment groups. If any significant difference exists between any two treatments at the 5% level ($p \leq 0.05$), the variable will be used as a covariate in the repeated measures analysis of covariance (ANCOVA) as described in this section to adjust for any pre-intervention difference between treatment groups.

In all analyses, careful attention will be given to the appropriateness of the statistical procedure by determining whether necessary conditions are satisfied; e.g., normality and equal variance. When conditions are violated, the use of data transformations intended to produce data that satisfy normality and equal variance assumptions will be explored. If an appropriate transformation cannot be found, non-parametric methods may be used as an alternative to the more standard analyses.

For all repeated measures ANCOVA of efficacy and pharmacodynamic endpoints, the SAS codes used will be similar to the following:

```
proc mixed data=xxx;
class subject day treatment;
model variable = baseline subject treatment day treatment*day;
repeated day / subject=subject type=csh;
lsmeans treatment*day / pdiff cl alpha=0.05;
ods output lsmeans=lsm;
ods output diffs=diff;
run;
```

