10.3.4.2 Efficacy - Daily Insulin Use

Hypothesis:

Multiple doses of REMD-477 will significantly decrease daily insulin use versus placebo treatment at Week 12.

The daily insulin use will be derived as the average daily insulin over a collection period ranging from either 3 or 7 days. For the Lead-In Period (Part A – 14 to 28 days; Part B – 7 to 14 days), the average daily insulin use will be derived from a period of 14 days. For Days 1, 8, 15, and 22, the average daily insulin use will be derived from the individual insulin values over the next 7 days. For Days 50, 78, 106 and 134, the average daily insulin use will be derived from the individual insulin values over the next 3 days. Baseline assessment is the derived average daily insulin use during the Lead-In (Part A – 14 to 28 days; Part B – 7 to 14 days) period. The measurements will be summarized separately for Parts A and B by treatment group and timepoint along with changes and percentage changes from baseline. Figures of mean average daily insulin use, changes and percentage changes from baseline will be presented separately for Parts A and B by treatment.

The changes from baseline and percentage change from baseline measurements will be statistical analyzed separately for Parts A and B. The statistical analysis for the changes from baseline measurements will be used to test the primary hypothesis, while the statistical analysis for the percentage changes from baseline measurements will be used as a sensitivity analysis. A sequential stepwise hypothesis and a Hochberg testing procedure will be utilized to allow for multiple testing while preserving the overall significance level of the trial.

For Parts A and B separately a repeated measures ANCOVA will be used to compare the changes and percentage changes from baseline in daily insulin use between treatment groups for each timepoint. Dependent variables will be treatment, day, and the treatment by day interaction. The baseline variable will be used as a covariate. Covariates may be added to the above model depending on the results from the comparison of baseline characteristics as detailed in section [10.3.4.1](#)

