Although CGM will be conducted throughout the study from Dose 1 through EOS visit for safety monitoring and insulin use adjustments, the CGM data collected during the one week periods following Doses 4, 8, and 12 and during wash-out on Weeks 16 and 20 will be analyzed.

The ratio of average glucose obtained from the CGM at Day 78 (Week 12) and Baseline will be multiplied against the ratio of average daily insulin use obtained from the insulin diary at Day 78 (Week 12) and Baseline. This metric will be derived as described below and summarized by treatment.

$$\frac{\text{Average Daily Glucose from CGM at Week 12}}{\text{Average Daily Glucose from CGM at Baseline}} * \frac{\text{Average Daily Insulin Use at Week 12}}{\text{Average Daily Insulin Use at Baseline}}$$

For Parts A and B separately an ANOVA will be used to compare the values for the above metric between treatment groups. Dependent variables will be treatment. Covariates may be added to the above model depending on the results from the comparison of baseline characteristics as detailed in section 10.3.4.1.

The LS mean for each treatment will be presented. Also, the difference from placebo, the 95% CI of the difference from placebo, and p-value associated with the null-hypothesis of no difference will be produced.

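### Covariates beyond each endpoint's own baseline enter the efficacy models only if a baseline significance test between arms is positive; they should be fixed in advance

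*SAP*

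**What the plan says.** SAP 10.3.4.1 plans preliminary analyses of variance to "assess whether the baseline average daily insulin use and HbA1c levels among subjects are similar between the treatment groups". The trigger follows: "If any significant difference exists between any two treatments at the 5% level" (p ≤ 0.05), the variable becomes a covariate in the repeated measures ANCOVA.

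For the primary endpoint, SAP 10.3.4.2 has one unconditional and one conditional element.

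- Unconditional: "The baseline variable will be used as a covariate", and for this endpoint "Baseline assessment is the derived average daily insulin use during the Lead-In" period. The template code agrees: "model variable = baseline subject treatment day treatment*day".
- Conditional: "Covariates may be added to the above model depending on the results from the comparison of baseline characteristics", with a reference back to 10.3.4.1.

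The same conditional sentence appears in 10.3.4.3 to 10.3.4.6. In 10.3.4.6 baseline HbA1c is an unconditional covariate for the HbA1c endpoint. The product of the glucose and insulin ratios in 10.3.4.4 differs: "For Parts A and B separately an ANOVA will be used to compare the values for the above metric between treatment groups", with treatment as the only fixed term, so any covariate there is conditional.

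The protocol (Section 10, Analysis of Key Study Endpoints) has an analysis of variance with covariance adjustment where necessary. SAP Section 4 says that the SAP supersedes it.

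**The concern.** In a correctly randomised trial a significant baseline difference between arms is a chance event. The test therefore selects covariates by accidental imbalance, when what makes a covariate useful is how well it predicts the outcome. The final form of the primary model is unknown until baseline values are compared by treatment arm, and it may differ between Parts A and B.

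The rule is also loosely written. It names analyses of variance but triggers on any pair of arms, and these have different chance rates. Section 10.3.4.1 makes inclusion mandatory once the test is positive, while the endpoint sections make it optional. Some discretion therefore remains in the primary analysis. SAP Section 11 allows unblinded preliminary analyses to reach sponsor study teams, which is a further reason to close it.

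HbA1c could plausibly bear on insulin change. Section 7 of the protocol has all subjects titrate insulin to a glucose target, and in Part A ties an optional insulin reduction at randomisation to screening HbA1c. A test of balance takes no account of this.

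**Working it through.** **Inputs.** From SAP Section 8: CV about 36% (used as SD 0.36), difference 30%, power 0.8, alpha 0.05 (taken as two-sided), at least 22 per group needed, 25 per group per Part enrolled. From SAP Section 6: three arms, 1:1:1. Not in the documents: the partial correlation r of baseline HbA1c with change in insulin use, given baseline insulin use. It is treated as an assumption and varied.

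**1. The plan's own figure.** n = 2 × [0.36 × (1.960 + 0.842) / 0.30]² = 22.6, so 23 per group against the stated 22. The figure reproduces to within rounding. At n=25 the t-based power is 82.3%.

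**2. Which covariates are conditional.**

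| Model | Fixed | Depends on the test |
|---|---|---|
| Daily insulin use (primary) | baseline insulin use | HbA1c |
| HbA1c | baseline HbA1c | insulin use |
| CGM and seven-point glucose | baseline of that parameter | both |
| Product of ratios | none | both |

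**3. How often the rule triggers by chance.** With 3 × 25 subjects and pooled-variance pairwise tests, some pair differs when the range of the three means exceeds the t critical value (1.993 on 72 df). This is the probability that a studentised range for three means exceeds 1.993 × √2 = 2.819, which is 0.121. A simulation of 200,000 randomisations also gives 12.1%. If the overall F-test is the gate, the rate is 5.0%.

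- HbA1c enters the primary model: about 12% per Part (5% with the F-test).
- HbA1c enters in exactly one of Parts A and B: 2 × 0.121 × 0.879 = 0.213, about 21% (2 × 0.05 × 0.95 = 9.5% with the F-test).
- At least one variable enters the product-of-ratios model in a given Part: 1 − 0.879² = 0.227, about 23% if the two are independent; 22% if they correlate at 0.3.

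**4. Effect on error rate and power.** One-visit ANCOVA, own baseline always included, 10,000 simulated trials per setting, true effect 0.8 SD (the plan's 0.30/0.36 is 0.83):

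| r | Type I error, pre-test | Power, pre-test | Power, always adjusted |
|---|---|---|---|
| 0 | 5.2% | 79.0% | 78.7% |
| 0.3 | 4.8% | 80.2% | 82.6% |
| 0.5 | 4.6% | 81.2% | 88.8% |
| 0.7 | 3.8% | 82.8% | 96.9% |

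**5. The same on the plan's own inputs.** Residual SD = 0.36 × √(1 − r²), n=25 per group, two-sample t-test at two-sided 0.05:

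| r | SD | Power |
|---|---|---|
| 0 | 0.360 | 0.823 |
| 0.1 | 0.358 | 0.827 |
| 0.2 | 0.353 | 0.838 |
| 0.3 | 0.343 | 0.857 |
| 0.4 | 0.330 | 0.883 |

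**6. Whether a covariate can act in the code as written.** The template puts subject in the MODEL statement as a fixed effect, while the text of 10.3.4.2 calls it random. With 75 subjects the subject columns have rank 75, and the rank stays 75 when baseline and treatment are added. Any covariate that is constant within a subject, HbA1c included, is therefore aliased with subject.

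**The case against.** The variables and the threshold are written down in advance and use baseline data only. The most valuable covariate, the endpoint's own baseline, is already fixed. The two Parts are analysed separately, so a one-term difference between them upsets no pooled analysis. All of this stands, and it makes the point one of efficiency and pre-specification.

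The precision gain is also uncertain. No value of r is given, and eligibility limits HbA1c to between 7% and 10%, which may weaken any correlation. The 36% is the CV of the insulin requirement itself, so it is not the residual SD of change after adjustment for baseline insulin. The planned test is a repeated measures ANCOVA with Hochberg, not a two-sample t-test. This stands too, and the power figures are illustrations only.

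A reader might infer three stronger things that the documents do not support.

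- That baseline insulin use enters the primary model only after a positive test. It is unconditional in both text and code, as is HbA1c in the HbA1c model.
- That the 23% chance applies to the primary model. An insulin imbalance changes nothing there; the figure belongs to models in which both variables are conditional.
- That pre-testing inflates type I error. In the simulations it stays near 5% or falls below it.

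**Conclusion.** The concern holds for covariates other than the endpoint's own baseline. Whether HbA1c is in the primary model is left to a chance event, with a probability of about 12% per Part under pairwise tests or 5% under an overall F-test. The wording does not settle which of these applies. The product-of-ratios ANOVA is the most exposed, because all its adjustment is conditional.

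Validity is not threatened. The precision forgone on the primary endpoint is a residual variance share of about r²: 1% at r=0.1, 9% at r=0.3, 16% at r=0.4, and nothing at r=0. These results assume correct randomisation, 25 evaluable subjects per arm, equal variances, no dropout and independent Parts. The change is worth making because it is nearly free and settles the primary model before arms are compared.

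**What to change.** 1. Delete the preliminary-ANOVA covariate rule in SAP 10.3.4.1 and the conditional covariate sentences in 10.3.4.2 to 10.3.4.6. Keep baseline comparisons descriptive.
2. State that baseline average daily insulin use and baseline HbA1c are fixed covariates, whatever the observed balance, in the primary insulin model, the HbA1c model, the glucose models and the product-of-ratios model. Glucose models retain their own baseline as well. Say explicitly whether fasting and MMTT glucose in 10.3.4.3 belong to this group.
3. For the remaining PD endpoints (hormone levels and their challenge-test AUCs) keep own baseline only. The argument for HbA1c and insulin use does not extend to them.
4. Remove subject from the MODEL statement, leaving within-subject correlation to the REPEATED statement, and align the text. Without this the added covariates do nothing.

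The cost is SAP wording and one or two degrees of freedom per model. If HbA1c carries no information (r=0), the simulated loss is about 0.3 percentage points of power (79.0% to 78.7%).

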Subject will be used as a random effect. The least squares (LS) mean for each treatment will be presented for each timepoint. Also, the difference between treatments, the 95% confidence interval (CI) of the differences, and p-value associated with the null-hypothesis of no difference will be reported for each timepoint where applicable based on the sequential testing methods as described below.

Step 1: The first step of the sequential testing will consist of a test for the effect of REMD-477. The Hochberg procedure will be used to assess the statistical significance of two tests: one for the superiority of 70 mg REMD-477 compared to placebo, the other for the superiority of 35 mg REMD-477 compared placebo. If the larger of the two p-values is less than the significance level (ie, 0.05), then both tests are considered to have reached statistical significance. Otherwise, if the smaller of the two p-values is less than half of the significance level (ie 0.025), then the corresponding test is considered to have reached statistical significance.

Step 2: If at least one of the two doses of REMD-477 is found to be superior to placebo, then the two doses of REMD-477 will be compared using the same significance level as that used to claim significance of either dose of REMD-477.

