10.4.4 Electrocardiogram

The ECG data will be obtained directly from the 12-lead ECG traces. These data include the QT interval calculated using the Bazett correction (QTcB), the QT interval calculated using the Fridericia correction (QTcF), the PR and QT intervals, the QRS duration, heart rate, and RR.

The ECG data will be summarized separately for Parts A and B by treatment, together with changes from baseline (see Section 10.1.1 for definitions of baseline). Figures of mean ECG data and mean change from baseline profiles will be presented separately for Parts A and B by treatment. The relationship between plasma concentrations of REMD-477 and changes from baseline in QTcF and QTcB will be explored graphically.

An outlier analysis will be performed including all individual post-dose QTcF and QTcB measurements (not the mean data), including all repeat and unscheduled readings. The frequency of subjects with a maximum increase from baseline in QTcB and QTcF intervals will be summarized for each treatment according to the following categories: >30 to 60 ms, >60, and \leq 30 ms. All incidences of >30 to \leq 60 ms, and >60 ms will be flagged on the listing. In addition, the frequency of subjects with QTcB and QTcF post-dose values will be summarized for each treatment, according to the following categories: >450 to 480, >480 to 500, >500, and \leq 450 ms. All incidences of >450 to 480, >480 to 500, and >500 ms will be flagged on the listing.

For Parts A and B separately the change from baseline of QT interval will be analyzed with a repeated measures ANCOVA. Dependent variables will be treatment, timepoint and the treatment by timepoint interaction. The change from baseline of the RR interval will serve as a covariate. Day is fitted as a repeated measure within subject. The estimated treatment means of the change from baseline of QT interval when change in RR interval equals zero will be presented for each timepoint. Also, the difference from placebo, the 95% CI of the difference from placebo, and p-value associated with the null-hypothesis of no difference will be presented for each timepoint.

An example of the SAS codes (abbreviated) is shown below:

```
proc mixed data=xxx;
  class subject day trtan;
```

```
model chg = chg_rr subject trtan day treatment*day;
repeated day / subject=subject type=csh;
lsmeans trtan*day / pdiff cl alpha=0.05;
estimate 'Est_CFB RR=0' intercept 1 chg_rr 0 trtan 1 0 avisit 1 0 0
trtan*avisit 1 0 0 0 0 0 /e;
...
run;
```

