A similar analysis will be performed using the change from baseline in QTcF. Dependent variables will be treatment, timepoint, and the treatment by timepoint interaction. The baseline QTcF will serve as a covariate. Day is fitted as a repeated measure within subject. Treatment LS means will be presented for each timepoint. Also, the difference from placebo, the 95% CI of the difference from placebo, and p-value associated with the null-hypothesis of no difference from placebo, will be presented at each timepoint.

An example of the SAS codes is shown below:

```
proc mixed data=xxxx;
class subject day trtan;
model chg = base subject trtan day treatment*day;
repeated day / subject=subject type=csh;
lsmeans trtan*day / pdiff cl alpha=0.05; run;
```

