12 CHANGES FROM THE PROTOCOL SPECIFIED STATISTICAL ANALYSES

The product of the ratio of average glucose obtained from the CGM at Day 78 (Week 12) and Baseline; and the ratio of average insulin use obtained from the insulin diary at Day 78 (Week 12) and Baseline, were not statistically analyzed with repeated measures ANCOVA since this is not a metric assessed at multiple timepoints. The definition of a hypoglycemic event was updated after the 1st interim of Part A to be defined as an incident where the glucose value obtained from the CGM in a previous timepoint is higher than 70 mg/dL, but drops to 70 mg/dL or less in the subsequent timepoint with the low CGM glucose reading lasting at least 10 minutes.

Additional analysis of the LDL cholesterol data has been added.

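### The SAP text makes subject a random effect, but its PROC MIXED template makes it fixed, and that code cannot estimate the Week 12 arm differences

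*SAP*

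**What the plan says.** SAP 10.3.4.2 tests the primary hypothesis with a repeated measures ANCOVA of change from baseline in daily insulin use. The model has treatment, day, their interaction and baseline as covariate, and the text adds "Subject will be used as a random effect". The same statement appears in SAP 10.3.4.3 to 10.3.4.6, 10.4.2 and 10.4.3. For insulin use the model is to give LS means, arm differences, 95% intervals and p-values by timepoint. The two comparisons with placebo go into the Hochberg step.

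SAP 10.3.4.1 prints one template for all efficacy and pharmacodynamic models of this kind, introduced with "the SAS codes used will be similar to the following". Subject is in CLASS, and the MODEL line is "model variable = baseline subject treatment day treatment*day". There is a REPEATED statement with `type=csh` and no RANDOM statement. The same MODEL line recurs in 10.4.2 (LDL) and 10.4.3 (vital signs).

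The ECG code in 10.4.4 follows the pattern. The QT example has "class subject day trtan" and "model chg = chg_rr subject trtan day treatment*day"; the QTcF example has "model chg = base subject trtan day treatment*day". The ECG text does not call subject random; it says "Day is fitted as a repeated measure within subject". Protocol Section 10 (Safety Analysis) does specify a random subject effect for QT and QTcF. SAP Section 12 does not list that change, although it records other departures, such as "Additional analysis of the LDL cholesterol data has been added".

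**The concern.** In PROC MIXED an effect in the MODEL statement is fixed. In a parallel-group trial subjects are nested in arms, so a fixed effect for every subject leaves no between-subject information with which to compare arms. The quantities lost are the ones that the primary test needs.

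If this is not settled first, the repair to the primary model would be chosen after the code fails on trial data. The repair is also not unique, because text and code together allow three covariance models:

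- heterogeneous compound symmetry alone (the code);
- a random subject effect with an unstated residual structure (the text);
- both combined.

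**Working it through.** **The plan's own figure.** The SAP gives no figure on estimability. Its only computed figure for this endpoint is the sample size (SAP Section 8). From the stated 36% CV, 30% difference, power 0.8 and alpha 0.05 (taken as two-sided), n = 2 × (1.960 + 0.842)² × (36/30)² = 22.6 per group. That rounds up to 23, against the stated 22. It is not in dispute here, and nothing below depends on it.

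**Inputs.**
- Three arms, 25 per arm in each Part (SAP Sections 6 and 8).
- Each subject is in one treatment group only (Protocol Section 3, Number of Subjects).
- Post-baseline insulin timepoints: Days 1, 8, 15, 22, 50, 78, 106 and 134 (SAP 10.3.4.2), so 8.

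**Why the contrast is lost.** Add a constant c to the 70 mg treatment effect and subtract c from the effect of every subject in that arm. No fitted value changes. LSMEANS gives each subject coefficient the weight 1/75, so:
- the 70 mg LS mean on any day moves by c − (25/75)c = 2c/3;
- the other two arms' LS means move by −c/3;
- the 70 mg minus placebo difference moves by c.

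The data therefore cannot determine these quantities. The same argument applies to each arm. It does not depend on the sample size, on missing records or on the covariance structure, because estimability depends only on the fixed-effects matrix.

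**Matrix check, insulin use, code as printed.**
- Rows: 75 × 8 = 600.
- Columns: 1 intercept + 1 baseline + 75 subject + 3 treatment + 8 day + 24 interaction = 112.
- Rank: 75 + 3 × (8 − 1) = 96. The subject columns alone have rank 75, and adding intercept, baseline and treatment leaves it at 75.
- Estimable: 0 of 24 LS means and 0 of 24 same-day differences. The baseline slope is not estimable either. Changes between days within an arm, and arm differences in such changes, remain estimable.
- With subject removed from MODEL: 37 columns, rank 25; 24 of 24 and 24 of 24 estimable.

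**Illustration on simulated data.** Two solutions of the printed model with the same residual sum of squares (16841.435) gave 70 mg minus placebo at Week 12 as −13.26 and −17.41. With subject removed, both solutions gave −13.68.

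**Other cases.** The HbA1c, LDL, vital-sign and ECG timepoints are those in the Part B schedule.

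| Model | Timepoints | Rank | LS means estimable as coded |
|---|---|---|---|
| Insulin, 22 per arm (528 × 103) | 8 | 87 | 0 of 24 |
| Insulin, 25 per arm, 15% of records missing at random | 8 | 96 | 0 of 24 |
| HbA1c | 3 | 81 | 0 of 9 |
| Seven-point glucose | 5 | 87 | 0 of 15 |
| LDL | 7 | 93 | 0 of 21 |
| Vital signs | 15 | 117 | 0 of 45 |

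**ECG.** The MODEL lines use `treatment`, and the QT example also uses `avisit`; neither is in CLASS. LSMEANS asks for `trtan*day`, but MODEL contains `treatment*day`. After correcting the names to `trtan` and `day`, 0 of 15 LS means are estimable for QT and 0 of 15 for QTcF. With subject also removed, 15 of 15 are estimable for each.

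**Covariance parameters at 8 timepoints.**
- `csh` alone: 8 variances + 1 correlation = 9.
- Random subject plus one residual variance: 2.
- Random subject plus `csh`: 10. The Jacobian of the 36 distinct covariance elements has rank 9 when the day SDs are equal and rank 10 when they are unequal.

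**Interval levels (minor).**
- The LDL and vital-sign code sets `alpha=0.10`, while the SAP text promises 95% limits, as does the protocol for heart rate and blood pressure. Limits at 90% are 1.645/1.960 = 0.839 times as wide.
- For QT and QTcF the protocol promises 90% limits and the SAP gives 95%. Section 12 does not list this.

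**The case against.** The strongest reply is that the code is only illustrative. The text gives a workable model and states the random subject effect in seven places, so the intent is clear. The SAP must be final before database lock. Section 12 mentions a first interim of Part A, so working programs may already exist. Failure would show as non-estimable output, and no bias, type I error or power effect has been shown.

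Most of this stands, and it limits the point to a specification error. It does not remove it. The text names no residual structure, so following the text alone does not fix the primary model.

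Three narrower objections also carry weight:

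- A random subject effect on top of `csh` is strictly redundant only when the day variances are equal. The advice against combining them rests on overlap and parsimony.
- The protocol's random subject effect covers heart rate, blood pressure, QT and QTcF. For insulin use the protocol specifies an analysis of variance, so it does not settle the primary model. Section 12 does not list that change of method either, which is a separate omission.
- The ECG text makes no random-effect claim, so the conflict there is with the protocol. The QT code is labelled an abbreviated example. `alpha=0.10` changes interval width, not p-values.

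**Conclusion.** The concern holds. SAP text and template code contradict each other on the primary model. Run as printed, the template gives 0 of 24 same-day arm differences for insulin use, including the Week 12 comparisons with placebo. With subject out of MODEL it gives all 24. The same fault affects the other efficacy and pharmacodynamic models, LDL and vital signs, and the ECG models once their variable names are corrected.

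The result rests on linear algebra and on each subject belonging to one arm; SAS itself was not run. No effect on the Day 78 standard errors is claimed, because that depends on a residual structure the SAP does not state. The ECG naming and interval-level items are minor. This should be corrected before database lock.

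**What to change.** 1. Delete subject from every MODEL statement (SAP 10.3.4.1, 10.4.2, 10.4.3 and both examples in 10.4.4).
2. Choose one within-subject covariance model and state it identically in text and code. One option is a RANDOM subject effect with a stated residual structure, for example independent residuals with day-specific variances. This keeps the SAP's random-effect statements and the protocol's safety-analysis wording. The other is the existing REPEATED statement with `type=csh` alone, with the random-effect sentences replaced. Do not combine the two by default.
3. Record in SAP Section 12 any departure from the protocol's random subject effect, including the present ECG wording.
4. Use `trtan` and `day` throughout the ECG code.
5. Set `alpha=0.05` in the LDL and vital-sign LSMEANS statements. For QT and QTcF, either use the protocol's 90% limits or list the change to 95% in Section 12.

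The cost is edits to SAP text, code and Section 12. Data collection and trial conduct do not change.

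### The repeated measures model described in the SAP has one baseline slope for all visits and may lose some precision at Week 12; adding baseline*day helps only once subject leaves the MODEL statement

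*SAP*

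**What the plan says.** SAP 10.3.4.1 gives one code template for every efficacy and PD repeated measures ANCOVA. Its CLASS line is "class subject day treatment", its MODEL line is "model variable = baseline subject treatment day treatment*day", and the within-subject covariance is set by "repeated day / subject=subject type=csh". It is offered as a pattern, not as final code: "the SAS codes used will be similar to the following".

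SAP 10.3.4.2 applies this to the primary endpoint. On baseline it says "The baseline variable will be used as a covariate" and mentions no interaction with day. On subject it says "Subject will be used as a random effect", which does not match the template, where subject is a CLASS variable listed among the fixed effects.

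The same section fixes the visits. "For Days 1, 8, 15, and 22, the average daily insulin use will be derived" over the following 7 days; "For Days 50, 78, 106 and 134, the average daily insulin use will be derived" over the following 3 days. That makes eight visits. The primary one is Day 78 (Week 12), and Days 106 and 134 fall after dosing has ended.

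**The concern.** A repeated measures ANCOVA that lets treatment vary by visit but not baseline assumes that change from baseline has the same slope on baseline at every visit. Several features of this trial make that doubtful:

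- The first four visits are 7-day means soon after lead-in; Day 78 is a 3-day mean eleven weeks later.
- Subjects titrate insulin to glucose targets throughout (protocol section 7).
- The protocol's dose rationale expects 10- to 30-fold accumulation, so the drug effect probably builds up and then washes out.
- The sample size states the effect as a percentage. If a 30% effect is proportional to baseline, the slope of change on baseline moves by -0.30 in the active arms once the effect is full.

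If the slopes differ, a common slope set largely by the early visits under-corrects chance baseline imbalance at Week 12. What is at stake is the width of the primary confidence interval.

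**Working it through.** **1. The plan's own figure.** SAP section 8: difference 30%, CV 36%, power 0.80, alpha 0.05 (taken as two-sided), 22 per group. n = 2 × (1.96 + 0.8416)² × (36/30)² = 22.6, so 23. Power at 22 is 0.789 by normal approximation (0.770 by t-test); at 25 it is 0.838 (0.823). The figure is reproduced to within one subject. It is an unadjusted two-group calculation that takes no credit for baseline adjustment.

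**2. The template read literally** (75 subjects, 3 arms, 8 days). Subject columns with the intercept have rank 75, day adds 7 and treatment*day adds 2 × 7 = 14, total 96. Baseline and treatment are constant within subject and add nothing: the rank is 96 with or without them. No baseline slope is identified and the 70 mg minus placebo contrast at Day 78 is not estimable. Adding baseline*day raises the rank by 7 to 103, and the contrast is still not estimable. With subject out of MODEL, both the slope and the contrast are estimable. Only then does the question of one slope or several arise.

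**3. Large-sample effect of a common slope, subject out of MODEL.** Assume equal SD at all visits, an additive drug effect, and correlation with baseline decaying exponentially from Week 1 to Week 12. The Week 12 slope of change on baseline is b12 = r12 − 1. The common slope bc is the limit of the fit under heterogeneous compound symmetry. The Week 12 variance ratio, common slope over own slope, is 1 + (bc − b12)² / (1 − r12²).

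| Correlation, Week 1 to Week 12 (assumed) | bc | b12 | Variance ratio | SE increase |
|---|---|---|---|---|
| 0.90 to 0.90 | -0.100 | -0.100 | 1.000 | 0% |
| 0.90 to 0.85 | -0.111 | -0.150 | 1.006 | 0.3% |
| 0.90 to 0.80 | -0.104 | -0.200 | 1.026 | 1.3% |
| 0.90 to 0.70 | -0.078 | -0.300 | 1.097 | 4.7% |
| 0.90 to 0.60 | -0.049 | -0.400 | 1.192 | 9.2% |
| 0.90 to 0.50 | -0.022 | -0.500 | 1.305 | 14.2% |

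Example, fourth row: 1 + 0.222² / 0.51 = 1.097. With an assumed proportional 30% effect, the SE change is -0.6% (0.90 to 0.90), 0.6% (0.80), 4.3% (0.70), 9.4% (0.60) and 15.5% (0.50).

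The result depends on how the fit weights visits. If the common slope were a plain average of the eight visit slopes, the 0.90 to 0.70 penalty would be about 0.5%, not 4.7%.

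**4. Size in units of dose.** The SD of the chance baseline difference between two arms is 36% × √(2/25) = 10.2% of mean dose. Multiplied by the slope gap, the typical uncorrected remainder is 0.096 × 10.2 = 1.0 point (correlation 0.80 at Week 12), 0.222 × 10.2 = 2.3 points (0.70) or 0.351 × 10.2 = 3.6 points (0.60).

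**5. Finite samples.** The simulations used 25 per arm, the eight SAP days, CV 36%, the same covariance structure and an assumed 20% day-to-day SD.

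- Drifting need, additive effect: common slope -0.05 to -0.09 against -0.15 to -0.38 at Week 12; variance 4% to 10% larger.
- Drifting need, proportional effect: -0.11 to -0.17 against -0.32 to -0.51; variance 7% to 18% larger.
- Other drift assumptions widen the range to 2% to 22%.
- Little or no drift: ratio 0.98 to 1.01.
- A pure random walk with an additive effect also gives a gain near zero, so drift alone is not sufficient.

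**6. What that is worth.** A ratio of 1.17 equals 25 × (1 − 1/1.17) = 3.6 subjects per arm, against the plan's margin of 25 − 22 = 3. A ratio of 1.02 equals 0.5. Power for a 30% difference hardly moves: with a proportional effect and correlation falling to 0.70, the SE is 6.65 against 6.38 and power 0.995 against 0.997; at 0.60, 7.76 against 7.10 and 0.972 against 0.988.

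**The case against.** The strongest reply is that the quoted line does not do what the concern describes. With subject fixed there is no baseline slope at all, so a reader who infers that the code adjusts Week 12 with a wrong slope is mistaken, and adding one term to that line repairs nothing. This stands. The point applies to the model in the text of 10.3.4.2, and the fix must start with the subject term.

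It also stands that the size rests on assumed inputs. Only the CV of 36% and the group size come from the documents; the correlations, the day-to-day SD and the drift do not. The losses under a proportional effect reflect a treatment-by-baseline pattern that a pooled baseline*day term captures only in part, and 10.3.4.2 already plans percentage change as a sensitivity analysis. The code is a template, and 10.3.4.1 provides for assumption checks and transformations.

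Extension to other endpoints is weaker still. Only insulin was simulated. In Part A, HbA1c is drawn after baseline only at Days 85 and 162, and the MMTT is done at Week 13, with Week 24 added only for subjects enrolled before Amendment 1. The mechanism of several early visits outweighing a late one is largely absent there.

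None of this is a reason to keep the single slope once the subject term has been corrected. It limits the point to a conditional gain in efficiency.

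**Conclusion.** The point holds as a modest, conditional refinement. Under the subject-random model, one baseline slope covers Days 1 to 134. If the relation to baseline weakens by Week 12, or the effect is proportional to baseline, the Week 12 variance is roughly 2% to 20% larger than it need be (SE about 1% to 10%). It is larger still only if the correlation falls to about 0.5. If the slopes do not differ, there is no gain, or a loss of about 1% to 2% of variance from the added term.

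Two stronger readings are not supported. A reader might infer that the primary comparison is biased. It is not: with complete data the estimate is the difference in mean change minus the slope times the baseline difference, and randomisation makes the expected baseline difference zero whatever slope is used. A reader might also infer that the stated power fails. It does not, because the sample size relies on no covariate adjustment.

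**What to change.** In the SAP 10.3.4.1 template:

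1. Take `subject` out of the MODEL fixed effects, so that the code agrees with the random-effect text in 10.3.4.2 and the Day 78 contrast becomes estimable.
2. Keep the REPEATED statement for the within-subject covariance.
3. Add `baseline*day`, giving `model variable = baseline treatment day treatment*day baseline*day`.

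State in 10.3.4.2, and for the other endpoints analysed by repeated measures at several post-baseline visits, that baseline enters together with its interaction with day. The glucose-insulin product in 10.3.4.4 is a single-timepoint ANOVA and needs no change.

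Cost: 8 − 1 = 7 fixed-effect degrees of freedom in the insulin model, out of about 75 × 8 = 600 observations per Part, and a negligible loss of precision if the slopes are in fact equal. The change should be made before database lock, by which time the SAP must be final.
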